5.1 Registration

Following evaluation and informed consent the patient will be registered. At the time of registration, the following information will be recorded:

1. Patient's name and medical record number
2. Patient's date of birth
3. Date of commencement of the protocol
4. Stage and Gleason score of prostate cancer
5. To which treatment arm patient is assigned

Eligibility criteria will be verified at the time of registration. A case number will be assigned following registration.

6.0 Study design

Study design

Double-blinded, parallel, placebo controlled randomized 2-group complete cross-over design with 12 week washout period.

Participant Assignment

Eligible patients will be randomly assigned to two groups in 1:1 ratio.

Group A will receive 6,000 IU daily of vitamin D3 (3 capsules of 2000 IU pills).

Group B will receive an identical placebo.

[figure not shown]
Each group will be comprised of approximately 50 patients. Patients who are not able to complete the study will be replaced.

Cross-over will be done after a period of 36 weeks followed by 12 weeks washout period. After 12 week washout period, patients on either arm will be crossed over to receive the drug on the other arm (patients who were on vitamin D arm will get crossed-over to receive placebo, while patients on placebo arm will be crossed-over to receive vitamin D).

They will be stratified randomization based on the Gleason score (less than or equal to 6, OR greater than 6) as well as the season of entry (winter/spring versus summer/fall). Seasonal stratification assignment will be based on the date of randomization:

If randomized between 12/22 and 6/21, it will be considered the winter/spring group and if randomized between 6/22 and 12/21 it will be the summer/fall group.

After completion of study, patient may choose to continue vitamin D if they desire.

Duration of the trial

Patients will be followed for 36 weeks after randomization followed by a washout period of 12 weeks and then be crossed over and followed for an additional 36 weeks (total 84 weeks). 103 patients are expected to enroll over an 11 year period.

Dose Modification:

- 1). If a patient's 25(OH) D3 level reaches > 200ng/ml with 6000 IU or 3 capsules a day, or any \geq grade 3 toxicity possibly related to cholecalciferol develops, 25(OH) D3 or placebo will be discontinued for 4 weeks. Treatment will then be resumed at lower dose of 4000 IU or 2 capsules a day. If a patient misses some period of time off the study drug, the treatment will be resumed such that the patient completes a total of 36 weeks on the study drug.
- 2). If a patient's 25(OH) D3 level reaches > 200ng/ml with the lower dose modification of 4000 IU or 2 capsules a day, or any grade 3 toxicity develops, 25(OH) D3 or placebo will be discontinued for 4 weeks. Treatment will then be resumed at lower dose of 2000 IU or 1 capsule a day.
- 3). If a patient's 25(OH) D3 level reaches > 200ng/ml with the lower dose modification of 2000 IU or 1 capsule a day, or any grade 3 toxicity develops, the patient will then be taken off study.
- 4). Patients that drop out after the first treatment period (36 weeks) will be included in the analysis but will require enrolling additional patients such that we have evaluable data on 100 patient-periods. An intention to treat analysis will be done.
- 5). If patient misses a daily dose of vitamin D3, or placebo, he should skip it and continue to take it as scheduled the following day. The patient should write down the day of the missed dose in the diary and should bring the diary with him on the day of physical. If patient misses more than 1/3 rd of the doses in a 12 week period, the patient will be taken out of the study and will be replaced by another patient.
- 6). At the end of study, patients may choose to continue taking vitamin D3 replacement per personal preferences.

6.1 Study Schedule: Pre-treatment evaluations are described in section 5.0 and are repeated here for sake of convenience.

Parameters	Pre-study ^e	4 weeks (+/- 7 days)	12 weeks (+/- 7 days)	24 weeks (+/- 7 days)	36 weeks (+/- 7 days)	4 weeks f/u ^a (+/- 7 days)
Physical Exam, Medical History, Vital Signs and ECOG(Wt, temperature, BP, pulse and respiration rate)	X			X		
Height	X					
Toxicity assessment	X	X^a	X	X	X	X^a
Serum alkaline phosphatase, aspartate aminotransferase (AST/SGOT), alanine aminotransferase (ALT/SGPT), total serum bilirubin, BUN, serum creatinine, electrolytes, calcium, phosphorous, total protein, albumin, glucose and LDH	X		X	X	X	
Serum 25(OH)D3	X		X	X	X	
PTH^b	X		X	X	X	
PSA	X		X	X	X	
24 hr urinary calcium and creatinine	X		X^g	X^g	X	
Assessment of infection, fall, fracture, thrombosis	X		X	X	X	
Investigational Biomarker samples^{b, c} and DBBR Blood Draw	X	X	X	X	X	
Radiographic study(Computed tomography and/ or bone scan)^f	X		X	X	X	
Study drug compliance assessment		X	X	X	X	
Nurse visit: ECOG, Wt, temperature & BP			X		X	

a- Telephone assessment

b- Performed in the lab. See Sec. 6.1 "Monitoring"

c- DNA, serum, plasma isolated through ongoing Vitamin D assessment protocol (only for patients at Roswell Park).

d- After a wash-out period of 12 weeks, patients will be crossed over. Patients would be followed every 12 weeks with similar plan.

e- Pre study evaluations are to be done within 4 weeks of registration. Complete history to be done at pre study evaluation.

f- If clinically indicated. CT/Bone scan to be done at the clinician's discretion.

g- Needed only if serum Ca level increases and it is per clinician's discretion.

All evaluations should be done within 4 weeks of registration unless otherwise noted.

1. Signed written informed consent. Roswell Park patients will have the option to participate in DBBR/Vitamin D trial.
2. Complete medical history, including diagnosis of prostate cancer, concurrent illness and concomitant medications.
3. Physical examination, including weight, height, ECOG performance status, temperature, vital signs (blood pressure, pulse and respiration rate), and digital rectal examination by patient's urologist
4. Serum alkaline phosphatase, aspartate aminotransferase (AST/SGOT), alanine aminotransferase (ALT/SGPT), total serum bilirubin, BUN, serum creatinine, electrolytes, calcium, phosphorous, total protein, albumin, glucose and LDH; Tumor biomarkers: PSA
5. Imaging studies for potential evaluable disease sites as clinically indicated
6. Baseline toxicity evaluation to document baseline symptoms
7. 25(OH) D3 level
8. 24 hour urinary calcium and creatinine
9. Research labs (PTH, serum/DNA/Plasma samples).
10. All pretreatment PSA values done up to 2 years prior to enrollment will be recorded.

Toxicity assessment will be done after 4 weeks of enrollment via a telephone assessment, thereafter would be done on every 12 week basis at clinic visit. Doses remaining will be assessed at each clinic visit and compliance ensured by telephone check by clinical research Coordinator. Laboratory data (as pre-study evaluation) will be repeated every 12 weeks. Investigational biomarkers will also be done with these laboratory tests on every 12 weeks basis.

Patients will continue on treatment for 36 weeks and then will have a 12 week washout period where they will be off any study drug or placebo. After 12 week washout period, patients will be crossed-over with follow up every 12 weeks for another 36 weeks (total =84 weeks) with assessments similar to those done at 36 weeks follow-up visit.

Prior studies have used similar design and there are substantial data that indicate that 36 weeks is a time period over which modification of PSA slope can be assessed.^{65, 66} In extensive vitamin D literature there are substantial data to indicate that "equilibrium" is achieved in 25(OH)D3 levels after a 12 weeks equilibration period. The literature indicates that 3 months is adequate "washout" to re-establish serum levels.^{60, 61} The half-life of 25(OH)D3 in the circulation is reported as \approx 1 mo in humans, the results for the submariners suggest a 2-mo half-life.^{67, 68} Conventional pharmacology indicates it should take 4 half-lives before a drug's equilibrium is achieved. Unlike a conventional drug, 25(OH)D3 is a metabolite whose concentration can be altered through balance between its production and clearance so that an equilibrium can be achieved earlier than would be expected from the half-life.^{69,70}

Monitoring

Parameters noted in the above table will be assessed as per standard clinical laboratory procedures. 25(OH) D3 levels will be measured in the hospital chemistry laboratory and are the standard measure for determination of vitamin D health. PTH levels after basal level will be measured as a research test in the lab of [name].

Procedure for collecting serum samples for PTH measurements.

Collect 5 mL blood in a red top tube (no additives). It is recommended that all samples to be collected A.M (to avoid diurnal variation issues). Blood samples are spun in a refrigerated centrifuge at 2000 x g for 10 min. Divide serum into two aliquots of 1.0 mL each/ patient (this avoids repetitive freezing and thawing every time the assay is performed). Freeze immediately at -70°C in plastic tubes. Under these storage conditions PTH is stable for up to 11 months.

Please call [name] to notify [name] lab of impending sample or if there are questions.

In addition all patients will be offered to enroll, after informed consent, on the DBBR-vitamin D repository trial.

PSA Measurement

Once enrolled on study, individual patients should get their PSA drawn at the same laboratory to ensure correct calculation of PSA dynamics for that individual.

Correlative/Special Studies

Blood samples will be collected and stored for future studies by the RPCI Data Bank and BioRepository (DBBR) for Roswell Park patients only, per Standard Operating Procedures for vitamin D trial banking. The DDBR is a shared resource (RPCI protocol I 03103), where participants are consented to donate blood for research (prior to and following treatments), to complete an epidemiologic questionnaire, and to give permission to have their blood specimens linked to the questionnaire and clinical data including diagnosis and laboratory test results for research. Collected biospecimens and/or data are provided to investigators with RPCI IRB approved research protocols.

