1.4 Vitamin D Supplementation and Toxicity

Supplementation with vitamin D has been studied in normal individuals and those with vitamin D deficiency. Recommended daily allowance of vitamin D is 400 IU. Considerable data suggests this may be inadequate to bring and maintain serum vitamin D levels in normal range.[Hollis et al] The currently accepted normal range of 25(OH) D3 is 32-100ng/mL [ng/ml X 2.5 ≈ nmol/L]. Supplementation with 10 µg (400 IU) of vitamin D raises 25(OH) D by only ≈0.45 nmol/(L µg day).

- Various studies report that one minimal erythema dose(Exposure of the body in a bathing suit to sunlight that causes a minimum redness to the skin) of UV-B radiation to the whole body produces between 10,000 and 25,000 IU (250 and 625 µg) of cholecalciferol and is safe.⁵⁷ Indeed, a continuing daily oral intake of 10,000 IU produces a mean serum 25OHD value approximating what is seen naturally after extensive summer sun exposure at mid latitudes.⁵⁸
- All instances of vitamin D toxicity have involved serum 25(OH) D concentrations more than 250nmol/L, a value that would be produced only at continuing oral intakes in excess of 10,000IU (250microg)/day.⁵⁹
- To attain a steady state of equilibrium in serum Vitamin D level, at least 3 months are required post a change in vitamin D supplementation dose.⁶⁰ The graph below depicts the same with varying doses of oral vitamin D supplementation.⁶¹
- The serum 25 (OH) D concentrations is maintained within a narrow range ≈75–220 nmol/L across a wide range of D3 intake: 20 µg (800 IU) to 500 µg (20000 IU)/d. The following graph clearly demonstrates that it is very safe to treat patients with vitamin D up to dosage of 10,000 IU-especially if 25(OH)D3 levels are monitored.⁵⁶ The serum levels appear to plateau between 120-130 nmol/L. Several studies have demonstrated the essential safety of continuous daily dosing with 4000, 5000 and 10,000 IU/day (100, 125 and 250 µg/day) for up to 16 weeks, and of 50,000 IU (1250 µg)/day for 8 weeks, all without evidence of toxicity.^{62 63 64}

[figure not shown]

Figure 4. Effect of the duration of vitamin D supplementation on the mean serum 25-hydroxyvitamin D [25(OH)D] concentration achieved. Vitamin D intakes for the groups were as follows: 10 µg (400 IU)/d (+; 28), 25 µg (1000 IU)/d (X; 28), 50 µg (2000 IU)/d (□; 64), 250 µg (10000 IU)/d (28).

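### The 25(OH)D3 action level of 200 ng/ml is twice section 1.4's own benchmark, without explanation, so a reading of 100–200 ng/ml prompts no level-based action

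*Combined protocol and SAP*

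**What the plan says.** The Dose Modification rules appear twice, in the Study Summary and in section 6.0. Item 1 applies when a patient's "25(OH) D3 level reaches > 200ng/ml with 6000 IU or 3 capsules a day", or when a possibly related toxicity of grade 3 or higher develops. Capsules are then stopped for four weeks and restarted at 4000 IU. Item 2 uses the same 200 ng/ml at 4000 IU, with another hold and a step to 2000 IU. Item 3 uses it again at 2000 IU and takes the man off study. No lower level is tied to any action, and nothing in the document explains the choice of 200.

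Section 1.4 supplies the benchmarks. It states: "The currently accepted normal range of 25(OH) D3 is 32-100ng/mL", with a factor of 2.5 to convert to nmol/L. It also states: "All instances of vitamin D toxicity have involved serum 25(OH) D concentrations more than 250nmol/L", and calls that level "a value that would be produced only at continuing oral intakes in excess of 10,000IU (250microg)/day". It describes doses up to 10,000 IU as very safe, "especially if 25(OH)D3 levels are monitored". Under section 6.1 the level is measured before the study and at weeks 12, 24 and 36 of each treatment period, with serum calcium at the same visits.

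**The concern.** The background section offers level monitoring as part of the safety case, and it gives one figure, 100 ng/ml, that is both the top of normal and the floor of reported toxicity. The operating rule then waits for twice that figure. A man reading 180 ng/ml on 6000 IU/day would stay on full dose as far as the level rule is concerned, and nobody is told to ask why.

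What is at stake is early warning in a few unusual men. A reading far above what the dose should produce may mean excess dosing, outside supplements (barred by section 4.1, item 8), heavy sun exposure or an atypical response. The primary endpoint and the power statement are not affected.

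**Working it through.** **Inputs.** Trigger 200 ng/ml (section 6.0, items 1–3). From section 1.4: factor 2.5, normal range 32–100 ng/ml, toxicity benchmark 250 nmol/L, slope, plateau and range. Entry ceiling 40 ng/ml (section 4.0, item 6).

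**1. Check the conversion factor.** Section 1.3.2 equates 40 nmol/L with 16 ng/ml: 16 × 2.5 = 40. The factor agrees.

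**2. Put trigger and benchmark in the same units.**
- Trigger: 200 × 2.5 = 500 nmol/L.
- Benchmark: 250 / 2.5 = 100 ng/ml, which is also the top of the normal range.
- Ratio: 500 / 250 = 2.0.

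**3. Average level expected on the trial dose.** Section 1.4 says that 10 µg (400 IU) "of vitamin D raises 25(OH) D by only" about 0.45 nmol/L per µg per day. Since 400 IU is 10 µg, 1 µg is 40 IU. Rise in ng/ml = (IU / 40) × 0.45 / 2.5. Starting from the entry ceiling of 40 ng/ml:
- 6000 IU: 150 µg × 0.45 = 67.5 nmol/L = 27 ng/ml, giving 67 ng/ml.
- 4000 IU: 100 µg × 0.45 = 45 nmol/L = 18 ng/ml, giving 58 ng/ml.
- 2000 IU: 50 µg × 0.45 = 22.5 nmol/L = 9 ng/ml, giving 49 ng/ml.

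**4. Cross-check with section 1.4's other figures.** "The serum levels appear to plateau between 120-130 nmol/L" is 120 / 2.5 = 48 to 130 / 2.5 = 52 ng/ml. The range quoted for 800 to 20,000 IU/day tops out at 220 nmol/L, and 220 / 2.5 = 88 ng/ml. Both lie below 100 ng/ml.

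**5. Margins.** On 6000 IU/day, a trigger of 100 ng/ml lies 100 − 67 = 33 ng/ml above the highest average level in step 3. The present trigger lies 200 − 67 = 133 ng/ml above it, and is 200 / 88 = 2.3 times the top of the range in step 4.

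**6. Limits of the slope.** It is quoted for 400 IU/day and does not hold far up the dose scale. At 20,000 IU (500 µg) it gives a rise of 500 × 0.45 = 225 nmol/L. Even from an assumed baseline of 10 ng/ml (25 nmol/L) that reaches 250 nmol/L, above section 1.4's own 220. It is therefore used here only up to the trial dose, where its result lies above the quoted plateau. It describes an average and does not say how many men would exceed 100 ng/ml. The documents give no such share.

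**The case against.** The strongest reply is that an unexplained threshold is not an error, and that the route to harm is already covered. Section 8.1 attributes all reported side effects to hypercalcemia. Calcium and creatinine are drawn every 12 weeks. Section 7.0 discontinues for stones, grade 2 or higher hypercalcemia, attributed grade 3 or higher toxicity, or creatinine at least 2.5 times baseline. Remaining doses are checked at each visit, outside vitamin D is barred and non-compliance is a ground for discontinuation. Section 10.1.3 also contemplates further investigation of clinically significant laboratory abnormalities. All of this stands, and it is why the point is minor. But the section 7.0 clinical rules act once an effect has appeared, and section 10.1.3 does not require any follow-up of a high 25(OH)D3. The level could prompt the question earlier.

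A second reply is that a trigger of 100 ng/ml would also seldom fire. That is true, and proper for an outlier check. The difference is that 100 ng/ml has a meaning in the protocol's own evidence and 200 ng/ml has none.

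A third reply is that a high reading need not come from the study capsules. Section 1.4 credits one whole-body minimal erythema dose of ultraviolet light with 10,000–25,000 IU, so sun has to be among the causes considered. A hold alone may also treat the wrong thing. With the half-life of one to two months in section 6.1, a hold of about one month leaves roughly 50% (0.5^1) to 71% (0.5^(1/2)) of any excess. Both points are accepted and shape the fix.

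Three stronger readings are tempting, and the documents do not support them:
- **That toxicity is to be expected at 100–200 ng/ml.** Section 1.4 says toxicity has been seen only above 250 nmol/L, not that exceeding it brings toxicity. It also cites 50,000 IU/day "for 8 weeks, all without evidence of toxicity", without giving the levels reached.
- **That a level above 100 ng/ml cannot occur on 6000 IU/day.** Section 1.4's wording invites this, but the slope and plateau are averages and individual men can exceed them.
- **That 200 was meant in nmol/L (200 / 2.5 = 80 ng/ml).** Nothing in the documents settles this.

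**Conclusion.** The point holds as a minor design matter. The level trigger is 2.0 times the figure that section 1.4 gives as both the top of normal and the floor of reported toxicity. It is the same at all three dose steps, and no rationale is stated. Between 100 and 200 ng/ml, the range that starts where section 1.4 places toxicity, the monitoring on which that section leans leads to no level-based action.

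The factor of two and the missing rationale rest only on the protocol's own numbers and are certain. That a reading above 100 ng/ml marks an outlier rests on section 1.4's average slope and plateau, and on a baseline no higher than 40 ng/ml. No harm in the 100–200 ng/ml range is shown, and the other safety rules remain in force there.

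**What to change.** In the Study Summary and section 6.0:

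- **Items 1 and 2:** lower the level trigger to > 100 ng/ml (250 nmol/L), stating both units. When it is met, check the capsule count, ask about other vitamin D intake and sun exposure, and review the same-visit serum calcium. Then apply the existing four-week hold and dose step, unless an outside source is found and stopped.
- **Item 3 (2000 IU):** let > 100 ng/ml prompt the same checks, without automatic removal from study at that level.
- Leave the toxicity limbs and section 7.0 as they are.

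The cost is one wording amendment in two places and one new question to the patient. The level, calcium and remaining doses are already checked every 12 weeks, so no test or visit is added.

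There are three downsides:
- **A rare extra hold.** The schedule is 36 + 12 + 36 = 84 weeks. One hold makes it 88 and two make it 92. Only the week 12 and week 24 readings can lead to a hold, since week 36 ends dosing.
- **A lower dose in a few outliers.** Each man who steps down to 4000 IU lowers the mean vitamin D dose across 103 men by at most 2000 / 103 = 19 IU, or 19 / 6000 = 0.3%.
- **A small added chance of revealing allocation.** Level-triggered holds fall almost entirely in vitamin D periods. That is already so under the present rule, but a lower trigger would make such holds somewhat more frequent.

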There appears to be an inverse correlation between the mortality rate of prostate cancer and exposure to ultraviolet radiation (UVR) in the US population. An association between vitamin D deficiency and prostate cancer was reported by Ahonen *et al.* in a 13-year follow-up of 19 000 middle-aged men in the Helsinki Heart Study.²⁷ In this study, 149 cases of prostate cancer were identified and matched to 566 sample controls. The study showed that low circulating levels of 25(OH) D3 (<40 nmol l⁻¹ or 16 ng ml⁻¹) were associated with an increased risk of subsequent earlier onset and more aggressive progression of prostate cancer, especially before the age of 52.

UVR exposure has a significant protective effect in prostate cancer.³⁸ Luscombe *et al* showed that cancer patients with the lowest quartile of sun exposure developed cancer at a median age of 67.7 years compared with 72.1 years in patients in other quartiles.³⁹ Although the mechanism of this association is unclear, it is possible that increased cutaneous synthesis of vitamin D₃ increases the circulating levels of 25(OH) D3 and the subsequent formation of 1 α , 25(OH)₂D₃ in the prostate by prostatic 1 α -OHase (20). 1 α , 25(OH)₂D₃ then interacts with VDR in the prostate and induces cell-cycle arrest and apoptosis-suppressing cancer development.^{40 41 42} Populations in whom vitamin D levels are estimated to be low have a greater risk of prostate cancer and other cancers.⁴³ The greater risk of prostate cancer in Afro-Caribbean men indicates that one factor contributing to the genesis of prostate cancer might be vitamin D insufficiency.⁴⁴

1.3.3 Clinical Data:

Limited but intriguing clinical data suggest 1 α ,25(OH)₂D₃ alone or in combination with other agents may slow PSA rise in men with either androgen stimulated or castration resistant prostate cancer patients.^{45 46 47 48 49 50 51 52 53} NCCN guideline--

- We have reported an approximately 25% response rate (PSA) in men with castration resistant prostate cancer using a regimen of 12mcg calcitriol 3X/week [MTW] + dexamethasone [4mg SMTW].⁵⁴
- Gross *et al* using calcitriol and Vieth *et al* using cholecalciferol showed slowing of PSA increase in patients with androgen stimulated prostate cancer.^{46 55}

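### Study drug restarts after a fixed 4-week hold with no check of 25(OH)D3, calcium or recovery; by the protocol's own half-lives, a man held at 200 ng/ml would still be at about 100 to 145 ng/ml

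*Combined protocol and SAP*

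**What the plan says.** Section 6.0, Dose Modification, describes a stepwise reduction, and the Study Summary repeats it. Item 1 applies when the "D3 level reaches > 200ng/ml with 6000 IU or 3 capsules a day", or on a toxicity of at least grade 3 that may be related to cholecalciferol. Item 2 applies when the "D3 level reaches > 200ng/ml with the lower dose modification of 4000 IU or 2 capsules a day", or on a grade 3 toxicity. In both items the instruction is "25(OH) D3 or placebo will be discontinued for 4 weeks. Treatment will then be resumed at lower dose". Neither item attaches a laboratory result or a recovery condition to the restart, and no other section does so.

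The 6.1 schedule places 25(OH)D3 and chemistry (including calcium) before the study and at weeks 12, 24 and 36. Toxicity is assessed by telephone at week 4 and then at the 12-weekly visits. Nothing is scheduled for the end of a hold.

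The rationale text that follows the 6.1 schedule gives the half-life of 25(OH)D3 as about "1 mo in humans, the results for the submariners suggest a 2-mo half-life". It adds that equilibrium may arrive sooner than a half-life would suggest, without giving a rate, and it treats 3 months as a sufficient washout.

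Section 1.4 states: "The currently accepted normal range of 25(OH) D3 is 32-100ng/mL [ng/ml X 2.5 ≈ nmol/L". It also states: "All instances of vitamin D toxicity have involved serum 25(OH) D concentrations more than 250nmol/L".

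Section 7.0 lists reasons for discontinuation. They include genitourinary stones, hypercalcemia of at least grade 2, and toxicity of at least grade 3 put down to the study drug.

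**The concern.** A hold normally ends when something has been shown: the level has come down, or the event has settled. Here it ends when 28 days have passed. That period is no longer than one half-life on the protocol's own figures, and one third of the 3 months that the protocol elsewhere allows for serum levels to settle. No section justifies 4 weeks.

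The stake is participant safety rather than the primary PSA comparison. A man followed exactly as written could be re-dosed while his level is still at or above the one that section 1.4 associates with toxicity, or while a grade 3 event is still present. An unscheduled test is not forbidden, but none is required.

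**Working it through.** The protocol gives no predicted level at restart. The only stated figure to reproduce first is its unit conversion.

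1. **Units.** Section 1.4 gives nmol/L ≈ 2.5 × ng/ml. Section 1.3.2 equates 40 "nmol l⁻¹ or 16 ng ml⁻¹"; 40 / 2.5 = 16, so the two agree. Hence 250 nmol/L = 250 / 2.5 = 100 ng/ml, which is also the top of the stated normal range. The trigger of 200 ng/ml is 200 × 2.5 = 500 nmol/L.

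2. **Level at restart.** Inputs: starting level 200 ng/ml and a 28-day hold (section 6.0); half-life h of about 1 or 2 months (6.1 rationale text). Assumption: first-order decay. The fraction remaining is f = 0.5^(28/h). With simple decay the level is 200 × f. If only the rise above a 30 ng/ml baseline decays, it is 30 + 170 × f. The baseline is an assumption; entry requires a level below 40 ng/ml.

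| Half-life | f | 200 × f | in nmol/L | 30 + 170 × f |
|---|---|---|---|---|
| 1 month as 28 days | 0.500 | 100.0 | 250 | 115.0 |
| 1 month as 30.44 days | 0.529 | 105.7 | 264 | 119.9 |
| 2 months as 60.88 days | 0.727 | 145.4 | 364 | 153.6 |

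   The range is therefore about 100 to 145 ng/ml, or about 120 to 154 with the baseline and calendar months. The trigger is a level above 200, so under this model these are lower bounds. A start at 250 ng/ml gives 132 to 182.

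3. **Time to reach 100 ng/ml.** Going from 200 to 100 takes one half-life: about 30 or 61 days with simple decay, against a hold of 28.

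4. **A faster rate.** If the 12-week washout is assumed to hold four half-lives (84 / 4 = 21 days), f = 0.5^(28/21) = 0.397 and the level is 79 ng/ml, or 89 to 104 with a baseline of 16 to 40. The documents give no such rate.

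5. **How often the level branch arises.** Section 1.4 puts serum levels at about 75 to 220 nmol/L for intakes of 800 to 20000 IU a day, that is 75 / 2.5 = 30 to 220 / 2.5 = 88 ng/ml. It describes a plateau at 120 to 130 nmol/L (48 to 52 ng/ml). The trigger of 500 nmol/L is 500 / 220 = 2.3 times the top of that range.

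6. **Next scheduled draw.** A level found at week 12 leads to restart near week 16. If visits keep to the calendar, the next draw is at week 24, so 24 − 16 = 8 weeks after restart.

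7. **Toxicity holds.** The calculation in step 2 does not carry over, because a grade 3 event can occur at any level. Here the texts are set side by side. Section 6.0 holds and restarts after a grade 3 toxicity. Section 7.0 discontinues for grade 3 or worse that is put down to the drug. Neither refers to the other. The cases that section 7.0 clearly leaves to items 1 and 2 are men held on level alone and events judged only possibly related.

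**The case against.** The strongest reply is that the level scenario hardly fits the protocol's own pharmacology: at 6000 IU a day, section 1.4 leads one to expect 30 to 88 ng/ml, so a man above 200 ng/ml is unlikely and a second such hold at 4000 IU more so. That stands, and it limits the practical weight of the point.

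It also stands that the plan allows full-dose treatment at any level up to 200 ng/ml. A restart at a lower dose at 100 to 145 ng/ml is consistent with that tolerance, so the tension with 250 nmol/L is tied to the trigger as much as to the length of the hold.

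Several stronger readings are tempting and are not supported:

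- A reader might infer that men are restarted at a toxic level. Section 1.4 says that toxicity has been seen only above 250 nmol/L, not that every level above it is toxic, and it reports much higher intakes without evidence of toxicity.
- A reader might infer that the level is clearly above 100 ng/ml in every case. With a 1-month half-life and simple decay it is 100 to 106, which is not distinguishable from the line, and the 6.1 text leaves room for a faster fall.
- A reader might infer that 12 weeks pass before the next draw. After a level-triggered hold it is about 8 on the calendar schedule.
- A reader might infer that every unresolved grade 3 event leads to re-dosing. Section 7.0 may remove many of these men first.

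None of this supplies a restart condition. Doubt about the rate of decline is a reason to measure, not a reason to rely on the clock.

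**Conclusion.** The point holds at low severity. Items 1 and 2 restart study drug on time alone. For a man held on level, the protocol's half-lives and first-order decay put him at about 100 to 145 ng/ml at restart (about 120 to 154 with a 30 ng/ml baseline), at or above the 250 nmol/L mark in section 1.4. The upper end, from the 2-month half-life, is clear; the lower end is marginal. The result rests on the decay model, the assumed baseline and the reading of a month, and it applies to a branch that should be rare.

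For toxicity holds there is no comparable figure. The gap is that restart does not depend on recovery, and sections 6.0 and 7.0 conflict for grade 3 events attributed to the drug.

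**What to change.** Reconcile items 1 and 2, in both section 6.0 and the Study Summary, with the toxicity level in section 1.4, the half-lives in the 6.1 rationale text and the discontinuation criteria in section 7.0. State in those items the check on which restart depends, drawing on the 25(OH)D3, calcium and toxicity assessments that the trial already runs, and say which section governs a grade 3 event. Any level, grade or interval is for the clinical team to set; none is proposed here.

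The cost is protocol wording and, at most, one repeat of an existing blood test in the few men held.
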